10.2 Analysis of Secondary Endpoints

10.2.1 Key Secondary Efficacy Endpoint

The key secondary efficacy endpoint is VOD-free survival by Day +100 post-HSCT and will be analyzed using the same methods described in Section [10.1](#) for the primary efficacy endpoint in the ITT Analysis Set.

The following summary will be provided:

- Analysis of VOD-free survival by Day +100 post-HSCT

The following figure will be provided:

- Figure of VOD-free survival by Day +100 post-HSCT

10.2.2 Other Secondary Efficacy Endpoints

These other secondary efficacy endpoints will be tested without multiplicity adjustments, and nominal p-values will be reported. The ITT Analysis Set will be used for these analyses.

10.2.2.1 Incidence of VOD by Day +30 post-HSCT

The incidence of EPAC-assessed VOD by Day +30 post-HSCT will be compared between treatment arms using the CMH test stratified by 2 stratification variables for randomization (very high risk/high risk and pediatric/adults).

The following summary will be provided:

- Incidence of VOD by Day +30 post-HSCT

10.2.2.2 VOD-Free Survival by Day +180 post-HSCT

The secondary efficacy endpoint of VOD-free survival by Day +180 post-HSCT will be analyzed using the methods described in Section [10.1](#) in the ITT Analysis Set. For monitoring of VOD-free survival by Day +180 post-HSCT, the diagnosis of VOD through Day +100 post-HSCT will be made by EPAC, and the diagnosis of VOD after Day +100 post-HSCT will be based on investigator assessments.

The following summary will be provided:

- Analysis of VOD-free survival by Day +180 post-HSCT

The following figure will be provided:

- Figure of VOD-free survival by Day +180 post-HSCT

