**Table 4 Ascites Assessment**

Ascites Assessment by Ultrasound		Ascites Assessment for EPAC or Clinical Diagnosis of VOD a
Ascites at Baseline	Ascites Post-baseline	
Absent b	Absent	No
Absent	Present	Yes
Present c	Absent	Not Evaluable d
Present	Present	Not Evaluable
Not Evaluable e	Absent or Present or Not Evaluable	Not Evaluable
Absent or Present	Not Evaluable	Not Evaluable

a For diagnosis of VOD using the modified Seattle criteria.

b Ascites “absent” at baseline or any post-baseline ultrasound examination is defined as trace ascites or no ascites as determined by ultrasonography on the specified ultrasound examination.

c Ascites “present” at baseline or any post-baseline ultrasound examination is defined as the presence of any amount of free fluid greater than trace as determined by ultrasonography on the specified examination.

d Ascites “Not evaluable” in the context of ascites assessment for EPAC or clinical diagnosis VOD per modified Seattle criteria means that ascites cannot be used when determining whether or not VOD is present.

e Ascites “Not evaluable” at baseline or any post-baseline ultrasound examination means the measurement was not obtainable for any reason on the specified ultrasound examination

EPAC= Endpoint Adjudication Committee; VOD=veno-occlusive disease.

Note: Liver size and ascites must be confirmed by ultrasound as physical examination is insufficient to document these parameters. All imaging should be made available to the central imaging facility.

Defibrotide (JZP-381)  
Clinical Trial Protocol: 15-007 Version 4.0

Jazz Pharmaceuticals, Inc.  
20 August 2018

Note: Baseline values for weight and bilirubin level will be obtained within 24 hours before the first dose of conditioning regimen for the patients in the DP arm and on the day that conditioning begins for patients in the BSC arm. Baseline values for hepatic size and presence of ascites will be obtained during ultrasound examination at the screening visit.

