- k. Bilirubin must be assessed daily during hospitalization; other serum chemistry and hematology assessments may be performed a minimum of 3 times weekly and coagulation parameters may be assessed a minimum of once weekly at the discretion of the investigator (see [Section 7](#) for details) to ensure patient safety ([Appendix 6](#)). The investigator must document in medical records the rationale for eliminating any protocol-mandated blood tests.
- l. Bilirubin must be assessed twice weekly; other serum chemistry, hematology, and coagulation parameters may be assessed at the discretion of the investigator (see [Section 7](#) for details) to ensure patient safety ([Appendix 6](#)). The investigator must document in medical records the rationale for eliminating any protocol-mandated blood tests.
- m. These assessments are to be performed post-HSCT only.
- n. If a patient is discontinued early from the study, engraftment status can be reported at the Day+30 post-HSCT visit.
- o. Abdominal ultrasounds (see [Appendix 4](#)) will be performed to assess liver and ascites and may be performed more frequently than at the protocol-specified time points, as clinically indicated (e.g., if VOD is diagnosed). If possible, the spot at which the mid-clavicular line intersects with the lower costal margin should be marked with a surgical pen. The ultrasound during the screening visit can be completed after randomization (if required) but prior to baseline. The ultrasound at Day +180 post-HSCT is to be performed only if the patient's total bilirubin is  $>2.0$  mg/dL or the patient has signs/symptoms of VOD.
- p. Assessment of chronic GvHD includes examination of rash, mouth, eyes, gastrointestinal tract, liver function tests, lungs, joints and fascia, genital tract, and other symptoms, as clinically indicated.

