10.1 Analysis of Primary Endpoint

The primary efficacy endpoint is VOD free survival by Day +30 post-HSCT. An event for the primary efficacy endpoint is defined as VOD diagnosis (as assessed by EPAC) or death, whichever is earlier, up to Day +30 post-HSCT.

The time to event for the primary efficacy endpoint will be measured in days and will be calculated as described in Section [8.2.4](#) with the event date equal to the date of VOD diagnosis by EPAC, the date of death up to Day +30 post-HSCT, or the censoring date if no VOD or death occurred.

Subjects will be censored under the following conditions:

- No event by Day +30 post-HSCT:
 - If EPAC makes an assessment of ‘No VOD’ and the subject is still alive at Day +30 post-HSCT, the censoring date will be defined as earliest date of the last assessments available for the modified Seattle criteria components (total bilirubin, weight gain or ascites evaluation, hepatomegaly evaluation) or the last biopsy assessment, whichever is later. Only assessment dates occurring on or before Day+30 post-HSCT will be taken into consideration when censoring.
 - If the subject is still alive at Day +30 post-HSCT and has EPAC-assessed VOD after Day +30 post-HSCT, the censoring date will be Day +30 post-HSCT.
- Not evaluable by Day +30 post-HSCT:
 - If the EPAC makes an assessment of ‘Not Evaluable’ and the subject has not died by Day +30 post-HSCT, the censoring date will be defined as the last date at which VOD could be evaluated (as specified by the EPAC).
 - If the EPAC indicates the last date at which VOD could be evaluated is prior to HSCT, the censoring date will be Day +1 post-HSCT.
- Event occurs prior to HSCT:
 - If the EPAC indicates the date of VOD onset is prior to Day +0 post-HSCT or if the subject dies prior to Day +0 post-HSCT, the censoring date will be Day +1 post-HSCT because the subject was not at risk at the start of the observation period.
- Subject does not undergo HSCT:
 - The date of randomization will be used as Day +0 post-HSCT. The censoring date will be Day +1 post-HSCT.
- Rescue treatment:
 - If a subject in the BSC arm receives rescue treatment with defibrotide but VOD (as assessed by investigator) is not confirmed by EPAC (either EPAC made an assessment of ‘No VOD’ or ‘Not Evaluable’ by Day +30 post-HSCT or the EPAC

made an assessment of VOD but the VOD date is more than 3 days later than the rescue initiation date), the subject will be censored at the date of rescue initiation.

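### Day +180 VOD-free survival has no censoring rule of its own; the inherited Section 10.1 rule would drop well patients at about Day +100 and bias the Kaplan-Meier rate downward

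*SAP*

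**What the plan says.** For Day +180, SAP 10.2.2.2 says "VOD-free survival by Day +180 post-HSCT will be analyzed using the methods described in Section" 10.1, in the ITT set. It adds only who diagnoses VOD: EPAC through Day +100, the investigator afterwards.

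For a living subject with an EPAC call of no VOD, Section 10.1 says "the censoring date will be defined as earliest date of the last assessments available for the modified Seattle criteria components", listed as "total bilirubin, weight gain or ascites evaluation, hepatomegaly evaluation", or the last biopsy if that is later. It also caps the dates: "Only assessment dates occurring on or before Day+30 post-HSCT will be taken into consideration when censoring".

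Protocol 6.3.1.1 defines hepatomegaly by ultrasonography, and the note under Table 4 adds: "Liver size and ascites must be confirmed by ultrasound as physical examination is insufficient to document these parameters". Ultrasound is routine at Day +100 (Protocol 7.3.2, window -7 to 0 days). For the next visit, Appendix 1 footnote o says "The ultrasound at Day +180 post-HSCT is to be performed only if the patient's total bilirubin is" above 2.0 mg/dL or the patient has signs or symptoms of VOD. Other scans are as clinically indicated. Appendix 2 footnote k repeats the Day +180 condition for rescued patients.

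**The concern.** The component-date rule takes the oldest of three last dates. At Day +30 this costs little, because all components are assessed close to the landmark. At Day +180 one component, liver size by ultrasound, is not routinely assessed after Day +100.

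Taken together, the two documents make event-free follow-up after Day +100 depend on how the patient is doing. Well patients are censored early. Patients who later die or are diagnosed with VOD stay at risk until their event, and those scanned because they look ill stay until the scan. That is informative censoring created by the schedule. It affects outputs that Section 10.1 asks for: the Kaplan-Meier rate with its interval, the median, and a plot drawn to Day +180.

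**Working it through.** **1. Plan's own figures.** The documents state no Day +180 rate, event count or power. The Day +30 design figures reproduce: ln(0.86)/ln(0.72) = 0.459 against the stated hazard ratio of 0.46, and 68 events give 89.3% power (Schoenfeld, one-sided 0.025) against the stated 90%. This point disputes none of them.

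**2. Which date governs for a well patient.**

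| Component | Last routine assessment | Source |
|---|---|---|
| Bilirubin | Day +180 visit (±30 days) | Protocol 7.3.3 |
| Weight or ascites | Day +180 visit, by weight | Protocol 7.3.3 |
| Hepatomegaly | Day +100 ultrasound, Days +93 to +100 | Protocol 7.3.2 |

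The earliest is the Day +100 scan, or the Day +60 scan if Day +100 was missed.

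**3. Closed-form illustration.** Let d be the number of late events and s the number of event-free patients kept in by a late scan, with all scans after the last event. The product of (1 - 1/r) for r from d+s down to s+1 equals s/(s+d). So:

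- reported S(180) = S(100) × s/(s+d)
- true S(180) = S(100) × (1 - late-event share)

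Assumed, because the documents give no figures: 200 per arm and S(100) = 0.75, so 150 patients; 6% late events, so d = 9, leaving 141; 10% of these scanned for cause, so s = 14.1. The 75% resembles a two-arm average ((86 + 72)/2 = 79% at Day +30, × 0.95 = 75%). It cannot describe the BSC arm under the design, where 72% is assumed already at Day +30.

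- Truth: 0.75 × 0.94 = 70.5%
- 10% scanned: 0.75 × 14.1/23.1 = 45.8%
- 5% scanned: 0.75 × 7.05/16.05 = 32.9%
- 40% scanned: 0.75 × 56.4/65.4 = 64.7%
- None scanned: 0%, since everyone left at risk has an event

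**4. By arm, by simulation.** Inputs: 200 per arm; Day +30 event rates of 28% and 14% (SAP 4.6); assumed event rates in both arms of 5% on Days 31-100 and 10% on Days 101-180; for-cause scans on Days 150-180. The true values are 0.72 × 0.95 × 0.90 = 61.6% and 0.86 × 0.95 × 0.90 = 73.5%.

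| Day +180 estimate | BSC | DP |
|---|---|---|
| Event-free patients censored at Day +180 | 61.5% | 73.5% |
| Inherited rule, no late scans | 0% | 0% |
| Inherited rule, 10% scanned | 16% | 19% |
| Inherited rule, 30% scanned | 35% | 42% |

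With no late scans, about 13 BSC and 16 DP patients remain at risk after Day +101, against 136 and 163 with censoring at Day +180. Varying the assumptions (5-10% events on Days 31-100, 5-15% on Days 101-180, 10-30% scanned) gives 9-49% BSC and 10-58% DP, against true values of 55-65% and 66-78%. The curve before Day +93 is unaffected.

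**5. Treatment comparison.** With late hazards and scanning equal between arms, the base-case hazard ratio is 0.62 under one rule and 0.61 under the other. Differences across scenarios are at most about 0.02, and the log-rank Z barely moves.

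**6. Alternative reading.** Suppose the investigator's hepatomegaly entry at the Day +180 visit supplies the date. The visit may fall on Days +150 to +210. With the cap moved to Day +180, a patient seen after Day +180 falls back to about Day +100. Visits spread evenly over that window give 45% BSC and 53% DP in the base case. Visits confined to Days 165-180 give 58% and 70%, still below the truth because deaths count to Day +180 while event-free follow-up stops at the visit.

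**The case against.** The strongest defence is that Section 10.1 does not strictly transfer. Its trigger is an EPAC finding of no VOD, and EPAC stops at Day +100. It names a hepatomegaly evaluation rather than an ultrasound, and Protocol 7.3.3 lists hepatomegaly under VOD monitoring, plus liver palpation, for every patient at Day +180. The Table 4 note concerns diagnosis and does not define a censoring date. This stands to the extent that early censoring of every well patient is the natural reading and not the only one. The alternative is still biased (step 6), and if the rule does not transfer, no rule exists. Nor can intent be presumed: SAP 10.2.2.3 (non-relapse mortality) and 10.2.2.5 (VOD resolution) have their own Day +180 censoring rules. Protocol 9.8.1 reserves last-evaluation censoring for patients not followed to the landmark.

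A reader might also infer that 10.2.2.2 contradicts itself by assigning late diagnosis to the investigator. It does not: that sentence says who diagnoses an event and is silent on censoring.

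The magnitudes rest on assumed rates; that objection stands. Numbers at risk appear at 10-day intervals, so a collapse of the risk set would be visible, though not corrected.

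**Conclusion.** The concern holds as a specification gap with a predictable direction of bias. Following the cross-reference on its natural reading biases the Day +180 Kaplan-Meier rate, its interval and the curve downward, and the median may be reached spuriously. The illustration is about 46% against 70.5%, or 33% to 65% for 5% to 40% scanned. The size depends on the assumed Day +100 rate, late-event rate and scan share; the direction does not.

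A reader might infer that the treatment comparison is also invalid. The documents do not support that: the log-rank test and hazard ratio are little affected when late hazards and scanning are equal between arms. A difference in late scanning or ascertainment is possible in an open-label trial with investigator diagnosis after Day +100, but nothing in the documents shows one.

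Nor does the point reach the confirmatory tests. This is one of the other secondary endpoints, tested with nominal p-values (SAP 10.2.2), so alpha control for the primary and key secondary endpoints is untouched.

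**What to change.** Add to SAP 10.2.2.2:

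> For the Day +180 endpoint, a subject alive and without VOD (EPAC through Day +100, investigator thereafter) is censored at Day +180 if the last investigator VOD monitoring assessment is on or after Day +180 (a visit after Day +180 counts as complete follow-up to Day +180), and otherwise at the date of that last assessment. The ultrasound-based component dates of Section 10.1 are not used for censoring after Day +100.

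State also how events between an early Day +180 visit (Days +150 to +179) and Day +180 are handled, so that events and event-free follow-up cover the same period. Without this, a smaller version of the bias remains.

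The cost is a few sentences in the SAP and a small programming change. The rule uses assessments already scheduled at the Day +180 visit and needs no new data or procedure.

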10.2.2.3 Non-Relapse Mortality by Days +100 and +180 post-HSCT

The incidence of NRM by Day +100 post-HSCT will be compared between the treatment arms. NRM is defined as death that occurs after HSCT in subjects who were noted as having malignant primary disease on the disease history eCRF and who do not have primary disease relapse post-HSCT. Only subjects with malignant primary disease at baseline will be included in the analysis. The time to NRM is the number of days from the date of Day +0 post-HSCT to the date of NRM. If the subject has disease relapse, they will be censored on the date of relapse. If they do not have disease relapse and do not die by Day +100 post-HSCT then will be censored on the date of the Day +100 post-HSCT disease relapse assessment. If the Day +100 post-HSCT disease relapse assessment is missing, they will be censored on the date of the last disease relapse assessment performed. If a subject does not undergo HSCT, the subject will be censored at the date of Day +1 post-HSCT.

This analysis will be repeated for NRM by Day +180 post-HSCT. The following will be presented for NRM by Day +100 post-HSCT and by Day +180 post-HSCT:

- The number of subjects by treatment group who had an event and who were censored (either due to not having an event or for other reasons as described above).
- The p-value from a log rank test stratified by risk status and age group.
- The KM estimates of the NRM rate (%) with 95% CI.
- the KM estimate of median time to NRM in days (95% CI).
- The hazard ratio (95% CI) from a Cox proportional hazards regression model stratified by risk status and age group.
- A KM plot will be presented up to Day +180 post-HSCT for each treatment arm. The number of subjects at risk will be displayed at 10-day intervals.

The following summary will be provided:

- Analysis of non-relapse mortality post-HSCT

The following figure will be provided:

- Figure of non-relapse mortality post-HSCT

The following listing will be provided and will include the relapse status at each visit and the date of relapse if applicable:

- Listing of primary disease relapse

10.2.2.4 Incidence of VOD-associated MOD by Days +30 and +100 post-HSCT

VOD-associated MOD is defined for subjects as occurring if the investigator answers “Yes” to the question “Has the subject been diagnosed with VOD associated MOD?” in the eCRF. The number and proportion of subjects who develop VOD-associated MOD by Days +30 and +100 post-HSCT will be summarized and compared between the 2 treatment arms using a chi-square test.

The following summary will be provided:

- Summary of VOD-associated MOD

The following listing will be provided and will include the date of MOD and type of renal and pulmonary dysfunction:

- Listing of VOD-associated MOD

10.2.2.5 Resolution of VOD by Day +180 post-HSCT and Time to Resolution of VOD

Of those subjects who were diagnosed with VOD by Day +30 post-HSCT by the investigator, the proportion of subjects who have resolution of VOD by Day +180 post-HSCT will be summarized by treatment arm.

Time to resolution of VOD will be calculated as follows:

Time to resolution of VOD = [Date of VOD resolution] – [Date of VOD diagnosis by investigator]

If VOD does not resolve by Day +180 post-HSCT, the subject will be censored on the date of the Day +180 post-HSCT VOD resolution assessment. If the Day +180 post-HSCT VOD resolution assessment is missing, they will be censored on the date of the last VOD resolution assessment performed.

The following will be presented for VOD resolution by Day +180 post-HSCT:

- The number of subjects by treatment group who had an event and who were censored (either due to not having an event or for other reasons as described above).
- The p-value from a log rank test stratified by risk status and age group.
- The KM estimates of the NRM rate (%) with 95% CI.
- the KM estimate of median time to NRM in days (95% CI).
- The HR (95% CI) from a Cox proportional hazards regression model stratified by risk status and age group.
- A KM plot will be presented up to Day +180 post-HSCT for each treatment arm. The number of subjects at risk will be displayed at 10-day intervals.

The following summary will be provided:

- Analysis of VOD resolution by Day +180 post-HSCT

The following figure will be provided:

- Figure of VOD resolution by Day +180 post-HSCT

The following listing will be provided and will include whether or not VOD was resolved, the criteria met for resolution, and the date of resolution:

- Listing of VOD resolution

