**Figure 1. Study Diagram**

HSCT=hematopoietic stem cell transplant; VOD=veno-occlusive disease.

Patients will continue to be monitored for development of late-onset VOD through Day +180 post-HSCT. Patients who develop clinical signs and symptoms of VOD after hospital discharge/Day +30 post-HSCT will require more frequent monitoring, and re-admission to

Defibrotide (JZP-381)  
Clinical Trial Protocol: 15-007 Version 4.0

Jazz Pharmaceuticals, Inc.  
20 August 2018

the hospital will be at the investigator's discretion. For all patients, confirmation (i.e., yes/no) that the modified Seattle criteria for diagnosis of VOD (e.g., total bilirubin level, hepatomegaly, weight gain, and/or ascites) have been met must be entered into the IWRS to allow dispensation of defibrotide for rescue treatment of VOD.

To reduce potential bias considering the open-label design, an independent EPAC that is blinded to study treatment assignment will be established to confirm retrospectively whether a patient met the criteria for VOD by Day +30 post-HSCT or by Day +100 post-HSCT, using the modified Seattle criteria. The EPAC will review relevant electronic case report forms (eCRFs), results of diagnostic procedures, and ultrasound results; alternate etiology (e.g., viral hepatitis, acute GvHD) will also be considered during review of patient data.

Efficacy will also be assessed through monitoring of hepatic function for development of VOD, relapse of disease, VOD-associated MOD, resolution of VOD, and survival.

Other assessments include health-related quality of life, and hospitalization resource utilization. Measurement of biomarkers in blood indicative of potential predictive or diagnostic VOD and/or GvHD biomarkers will also be performed. Blood samples for measurement of defibrotide concentrations will be collected according to an intensive schedule from a subset of patients in the DP arm to characterize the pharmacokinetics of defibrotide for prophylaxis. The remainder of patients in the DP arm will follow a sparse schedule for collection of pharmacokinetic (PK) samples; and all patients who develop VOD and receive defibrotide for rescue treatment of VOD will also have fewer PK samples collected. Serum samples to assess the immunogenicity of defibrotide will also be collected in any patients receiving defibrotide either as prophylaxis or rescue treatment (irrespective of treatment assignment).

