### 6.3.3.3 **Veno-Occlusive Disease-Associated Multi-Organ Dysfunction**

Veno-occlusive disease-associated MOD is defined as renal or pulmonary dysfunction in the presence of VOD. Renal dysfunction will be diagnosed if any of the following criteria are met by Day +30, Day +100, or Day +180 post-HSCT:

- Serum creatinine  $\geq 3$  times the value at baseline or the lowest value during HSCT conditioning
- Creatinine clearance (CrCl)  $\leq 40\%$  of the value at baseline or the greatest value during HSCT conditioning, calculated using Cockcroft-Gault for adults and Schwartz formula for pediatric patients, or the glomerular filtration rate (GFR) (calculated if cystatin C is measured),  $\leq 40\%$  of the value at baseline or the greatest value during HSCT conditioning, ([Grubb et al. 2005](#); [Larsson et al. 2004](#)).
- Dialysis dependence  
Note: Renal dysfunction must be attributable to fluid overload or mechanical impingement from abdominal distention or hepatic enlargement and not due to nephrotoxic drugs (e.g., cyclosporine, amphotericin B).

Pulmonary dysfunction will be diagnosed if the patient requires oxygen supplementation using any of the following by Day +30, Day +100, or Day +180 post-HSCT:

- Face mask for at least 24 hours
- Bilevel positive airway pressure (BiPAP) device or
- Ventilator support  
Note: Oxygen supplementation by nasal cannula is not a criterion for pulmonary dysfunction. Pulmonary dysfunction must be attributable to fluid overload or mechanical impingement from abdominal distention or hepatic enlargement and not due to infection (e.g., pneumonia).

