4.3.2.3 Other Secondary Endpoints

Other secondary efficacy endpoints will be tested without multiplicity adjustments, and nominal p-values will be reported. Other secondary efficacy endpoints include the following:

- Incidence of VOD by Day +30 post-HSCT
- VOD-free survival by Day +180 post-HSCT
- NRM by Days +100 and +180 post-HSCT

- Incidence of VOD-associated MOD (ie, severe VOD) by Days +30 and +100 post-HSCT (in those subjects who develop VOD)
- Proportion of subjects who have resolution of VOD by Day +180 post-HSCT and time to resolution of VOD
- Incidence of VOD after Day +30 post-HSCT up to Days +100 and +180 post-HSCT
- Health-related quality of life using EQ-5D-5L (adults only), EQ-5D-Y (proxy version 1; pediatric subjects 4 to 7 years of age), and EQ-5D-Y (self-report version 1; pediatric subjects 8 to <16 years of age)
- Pharmacokinetics of defibrotide
- Safety of defibrotide in addition to BSC vs BSC alone, including AE profile, SAE profile, laboratory abnormalities, and vital signs
- Incidence of Grades 2, 3, and 4 acute GvHD by Days +30, +100, and +180 post-HSCT, and the incidence of chronic GvHD by Day +180 post-HSCT
- Graft failure and time to neutrophil and platelet engraftment

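### Severe VOD (VOD-associated MOD) is counted from an unblinded investigator's yes/no answer without EPAC-confirmed VOD, so its nominal between-arm comparison can be biased, by an amount and in a direction the documents do not fix

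*SAP*

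**What the plan says.** Protocol 6.3.3.3 gives the concept: "Veno-occlusive disease-associated MOD is defined as renal or pulmonary dysfunction in the presence of VOD". It lists renal and pulmonary criteria and requires a judgement of cause, but does not say whose VOD diagnosis counts. SAP 10.2.2.4 makes this operational: "VOD-associated MOD is defined for subjects as occurring if the investigator answers" yes to a single eCRF question. The proportions at Days +30 and +100 are then "compared between the 2 treatment arms using a chi-square test".

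For VOD itself the plan relies on blinded adjudication. Protocol 3.1 explains that, because the trial is open label, "an independent EPAC that is blinded to study treatment assignment will be established to confirm retrospectively whether a patient met the criteria for VOD". SAP 10.2.2.1 follows: "The incidence of EPAC-assessed VOD by Day +30 post-HSCT will be compared between treatment arms using the CMH test". EPAC also decides VOD for the primary endpoint (SAP 10.1), the key secondary endpoint (SAP 4.3.2.1 and 10.2.1), and the Day +180 and late-VOD endpoints up to Day +100 (SAP 10.2.2.2 and 10.2.2.6).

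Two statements about the denominator do not agree. SAP 4.3.2.3 lists the endpoint as "Incidence of VOD-associated MOD (ie, severe VOD) by Days +30 and +100 post-HSCT (in those subjects who develop VOD", while SAP 10.2.2 says of the whole group: "The ITT Analysis Set will be used for these analyses". On error control, SAP 10.2.2 says: "These other secondary efficacy endpoints will be tested without multiplicity adjustments, and nominal p-values will be reported".

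**The concern.** The trial reports a between-arm p-value for severe VOD that rests on unblinded judgement alone. Nothing in SAP 10.2.2.4 removes a patient whom EPAC classed as having no VOD, so the same patient can appear without VOD in one table and with severe VOD in the next.

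The risk need not be equal in the two arms. Protocol 5.7.6 bars BSC patients from defibrotide unless they are being treated for VOD, and Protocol 3.1 releases rescue drug once the site enters in IWRS that the modified Seattle criteria are met. A DP patient on prophylaxis is already receiving the same dosage (Protocol 5.3). The sponsor anticipates the problem elsewhere: the primary analysis censors BSC patients who were rescued without EPAC confirmation (Protocol 9.8.1, SAP 10.1), and Protocol 11.8 singles out unconfirmed BSC cases for review. MOD has no comparable rule and no EPAC-based sensitivity analysis. Concordance between investigator and EPAC (SAP 10.1.3) covers only VOD by Day +30.

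**Working it through.** **Stated figures.** The documents give no rate, power or sample size for MOD, so there is no planned MOD figure to reproduce. The design figures concern the primary endpoint and do reproduce: ln(0.86)/ln(0.72) = 0.459 for the hazard ratio, and 68 events give 89% power by Schoenfeld's formula against the stated 90%. Only the planned 200 per arm (SAP 4.6) is used below.

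**Inputs for an illustration with no true treatment effect.**
- v, true VOD in both arms: 20%, the control rate in the earlier paediatric randomised trial (Protocol 1.2; the defibrotide group had 12%).
- s, share of true VOD with MOD: 30%, an assumption. The nearest figure is 3 deaths from severe VOD among 10 VOD patients in a historical control group (Protocol 1.2), which is mortality, not MOD.
- q, share of BSC patients without VOD whom the investigator over-calls: 10%, an assumption. None is assumed in DP; equal over-calling and flagging in both arms would create no difference.
- r, share of over-called patients also recorded with MOD: 0% to 50%, an assumption.
- Two-sided 0.05 chi-square test, 200 per arm, 200,000 simulated trials.

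**Formulas.** With all randomised patients as denominator, MOD is vs in DP and vs + (1−v)qr in BSC. Here vs = 0.20 × 0.30 = 6.0%, and the over-called group is 0.80 × 0.10 = 8.0% of BSC. With investigator-diagnosed VOD as denominator, MOD is s = 30.0% in DP and [vs + (1−v)qr] / [v + (1−v)q] in BSC, where the denominator is 0.20 + 0.08 = 0.28.

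| r | BSC MOD, all randomised (DP 6.0%) | Test rejects (in favour of DP) | BSC MOD, investigator VOD (DP 30.0%) | Test rejects (in favour of DP) |
|---|---|---|---|---|
| 0% | 6.0% | 4.8% (2.4%) | 21.4% | 15.8% (0.2%) |
| 10% | 6.8% | 5.9% (4.8%) | 24.3% | 9.5% (0.4%) |
| 30% | 8.4% | 14.7% (14.5%) | 30.0% | 5.0% (2.3%) |
| 50% | 10.0% | 30.7% (30.7%) | 35.7% | 8.8% (8.2%) |

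**Reading the table.** In the first row over-called VOD adds no MOD, so the all-randomised comparison is unbiased. As r rises, the bias on that denominator always favours DP. On the other denominator the BSC rate is a weighted average of s and r, so it lies below the DP rate when r < s, equals it when r = s, and exceeds it when r > s. The sign of the bias therefore changes at r = 30% here.

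**Sensitivity.** With v from 12% to 20%, q from 5% to 20% and r from 10% to 50%, the all-randomised rejection rate runs from 5.0% to 91.7%. A range that wide shows that the size is undetermined; it is not an estimate.

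**After the fix.** If EPAC rejects the over-called cases, they leave the numerator. With equal MOD of 3%, 6% or 10% per arm, the test rejects in 4.8%, 4.6% and 4.8% of trials, about half of them in favour of DP.

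**The case against.** The strongest reply is that over-calling VOD does not by itself create an MOD event. The investigator must record MOD separately. The criteria in Protocol 6.3.3.3 are largely measurable (creatinine, creatinine clearance, dialysis, face mask for at least 24 hours, BiPAP, ventilator), and the dysfunction must be attributed to fluid overload or mechanical impingement rather than to nephrotoxic drugs or infection. This stands. A reader might infer that any dialysis or ventilation in an over-called patient counts as severe VOD; the protocol definition excludes that, although the attribution is made unblinded.

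It can also be said that no protection was removed, because Protocol 11.9.2 gives EPAC the primary and key secondary VOD endpoints and never mentions MOD. That is right. The point is that the VOD component of MOD is not tied to EPAC's existing finding.

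The difference in incentive is limited too. The IWRS entry is required in both arms. Prophylaxis ends by Day +30, with a recommended minimum reaching about Day +15 (Protocol 1.3), after which a DP patient also needs a diagnosis to receive study drug. Ultrasound confirmation of liver size and ascites (Protocol 6.3.1.1) and monitoring of IWRS entries (Protocol 11.8) reduce over-calling. These safeguards stand, but none changes how MOD is counted.

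**Conclusion.** The defect is in the text and needs no assumption: an EPAC finding of no VOD does not stop a patient counting as severe VOD, and no planned analysis shows the effect. That this can bias the comparison rests on unconfirmed diagnoses differing by arm, which the access rules make plausible but do not establish.

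Two stronger readings are tempting. One is that over-diagnosis in BSC necessarily becomes an apparent benefit of DP. The documents do not support it: a second investigator answer is needed, and under the denominator of patients who develop VOD the bias can run the other way. The other is a numerical size for the spurious difference or its share of a true effect. The documents supply neither rate, so the table above is an illustration only.

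The consequence is confined to a secondary endpoint outside the gatekeeping, reported with nominal p-values. Primary and key secondary conclusions are unaffected. The change is worth making because it is cheap and specific.

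**What to change.** In SAP 10.2.2.4:

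- Define the main endpoint as investigator-recorded MOD in a patient with EPAC-confirmed VOD by the same time point (Day +30, Day +100).
- State the ITT set as denominator, to match SAP 10.2.2, and align the wording of SAP 4.3.2.3.
- State a rule for EPAC 'Not Evaluable', for example no event in the main row and an event in a sensitivity row.
- Keep the investigator-only count as supportive, since early rescue might keep a patient from meeting EPAC's criteria.
- Tabulate MOD by EPAC result and arm at both time points.
- List the definition in SAP Section 5, and note that Protocol 9.8.3.4 refers to Section 6.3.3.2 (relapse) for a definition that stands in 6.3.3.3.

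The cost is SAP wording and one merge with the EPAC data, which already run to Day +100. No new data are needed, and the SAP's Purpose section leaves decisions open until database freeze. The downside is fewer MOD events in the main row. Attribution of organ dysfunction also remains unblinded, so the fix is partial.
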